7.1. RAPTOR f feasibility design

This is a multi-centre, open-label, randomised two-arm parallel feasibility study. Aiming to assess the feasibility of a full-scale randomised study of RAPID driven treatment of pleural infection versus standard care.

Once participants are diagnosed with pleural infection, based on well-recognised diagnostic criteria in accordance with the evidence-based recent national British Thoracic Society guidelines(BTS 2023)(1), they are allocated to either the standard care group, who receive pleural infection management as per BTS guideline 2023) (1), or the intervention group, who receive treatment which is driven according to the baseline calculated RAPID score (see below).

Participants with suspected pleural infection will be approached initially by the clinical team as inpatients. Enrolment will occur within 24 hours of confirmation of the diagnosis of pleural infection and / or chest drain insertion using standard criteria for the diagnosis of pleural infection as per BTS guidelines (1).

The RAPID score

For participants allocated to the RAPID driven treatment arm only, the risk stratification "RAPID score" will be calculated at the time of presentation according to the parameters in Table 1. According to the calculated RAPID score, subsequent treatment will proceed (see below).

Parameter	Me	asure	Score
R enal	Serum Urea Level	< 5 mmol/L	0
		5 – 8 mmol/L	1
		>8 mmol/L	2
A ge	Age	< 50 years	0
		50 – 70 years	1
		> 70 years	2
P urulence of fluid	Purule	ent fluid	0
	Non-pur	1	
Infection source	Communi	ty-acquired	0
	Hospital	-acquired	1
D ietary factors	Serum albumin level	>27mmol/L	0
		<27mmol/L	1
Risk categories	Low risk	Moderate risk	High risk
	0-2	3-4	5-7

Table 1:The RAPID risk–prediction score (7,12)

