	15. To assess if levels of pleural fluid and blood biomarkers (suPAR, PAI-1, IL 1+2, and NET) will predict treatment failure	15. The proportion of participants with an elevated level of pleural fluid and blood biomarkers in serial samples taken on day 1 (randomisation day), 3 and 5(post - randomisation) who did not respond to medical treatment.	15. During hospital stay and while the chest drain in situ (optional).
Intervention(s)	In the intervention arm, following randomisation, a baseline RAPID score will		

Intervention(s)

In the intervention arm, following randomisation, a baseline RAPID score will be calculated (see Table 1). According to the score, participants will be allocated into two groups, as outlined below. The subsequent treatment will be determined by the calculated RAPID score.

Low RAPID score group:

- Admission for drainage Therapeutic aspirate or short-term chest tube insertion for 24 hours and subsequent tube removal if there are no features of sepsis syndrome or significant residual collections, see predefined treatment failure criteria below.
- Early discharge home within 24 to 48 hours of admission if they meet the proposed discharge criteria (see page 26) and they will be provided with a 24/7 contact number for the clinical study fellow if they have any concerns.
- Review in clinic within 3days +/- 2 days, if any features of medical treatment failure are present, they will be admitted to hospital and treated as a medium-high risk score group.

Medium – high RAPID score group:

- Admission for drainage Chest tube insertion
- Intrapleural instillation of recombinant human deoxyribonuclease (DNAse) 5mg BD (diluted in 30mls sterile water) and Recombinant human tissue plasminogen activator (tPA, Alteplase) 5-10mg BD (diluted in 30mls sterile water) intrapleural immediately after chest drain insertion if deemed safe and no contraindication e.g. no active bleeding or bleeding disorder.

	 Surgical referral at time of chest tube insertion for consideration of Video Assisted Thoracoscopic Surgery (VATS) or open surgery. 	
Comparator	Standard care and intergroup comparison in the RAPID driven arm.	

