9.6. Blinding and code-breaking

There is no blinding in this study, hence no un-blinding procedures or code-breaking are required.

9.7. Description of study intervention(s), comparators and study procedures (post-randomisation and inpatient period)

Intervention arm

In the intervention arm, treatment will be determined according to the calculated baseline RAPID score.

Patients with a higher RAPID score (and thus higher predicted mortality and morbidity (7,12)) will be triaged to more aggressive treatment early in the disease, and those with lower predicted mortality and morbidity will be treated less aggressively.

A. Low risk (RAPID score 0 to 2):

Patients will be treated as follows:

- 1. Pleural drainage: therapeutic pleural aspiration (drain to dryness) using a Rocket kit will be suggested as the initial treatment. If the patient has already had a chest tube inserted prior to randomisation (as randomisation can occur for 24 hours after drain insertion), then patients will be admitted for drainage for a proposed maximum of 24 to 48 hours, with the removal of the drain as soon as possible, provided there is no residual collection of pleural fluid on the chest-xray (CXR) or thoracic ultrasound or CT scan before drain removal. No specific size of drain is specified, and local practice should be followed.
- 2. **Broad spectrum antibiotics**: see below for the expected standard of care in both intervention groups concerning antibiotics, which are as per NHS standard care for pleural infection. Use of early oral antibiotics to promote discharge is recommended in this group.
- 3. **Review at 3 days +_ 2 days post-discharge** with bloods including full blood count, CRP (Creactive protein), liver and renal profile, ultrasound scan and chest x ray.
- 4. **Patient contact:** All patients will receive a 24-hour contact number (to the study fellow) who can be contacted should there be any concern or deterioration when at home which will prompt urgent review by the pleural service locally.

If at any point a patient is considered to have *failed treatment* on the basis of predefined criteria (see below), they will then be treated as per the intermediate/high-risk group below and will be admitted to hospital.

B. Intermediate + high-risk (RAPID score 3 to 7)

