The intermediate and high-risk groups have been combined for the treatment algorithm; there are similar numbers of patients in the combined intermediate and high risk group and the low-risk group (7). Patients in this category will be treated as follows:

- 1. **Pleural drainage:** all patients will be admitted to hospital for chest drain insertion and remain in hospital for as long as is clinically required while the tube is in situ. No specific size of drain is specified, and local practice should be followed.
- 2. Broad spectrum antibiotics: see below; IV antibiotics can be given while the patient is admitted.
- 3. Adjunctive therapy:
 - a. Intrapleural enzyme therapy (tPA / DNase) should be started as soon as possible after drain insertion and randomisation, assuming there are no contraindications. if there is no risk of bleeding.

b. In parallel, referral to local thoracic surgical services made at the time of randomisation, and the need for surgery clinically revisited at 48 hours post-randomisation.

c. In patients where there are contraindications to intrapleural enzyme therapy, immediate surgical intervention in suitable patients should be considered.

Standard care arm:

In the standard care group, the RAPID score *will not be routinely calculated*, and all patients will undergo treatment as per current national guidelines (BTS 2023) (1). This is summarized as follows:

- 1. **Pleural drainage:** all patients will be admitted to the hospital for chest drain insertion and subsequent drainage
- 2. Broad spectrum antibiotics: see below
- 3. **Clinical review** of progression will occur 48 to 72 hours after randomisation and initial above treatment. If there is evidence of poor clinical response (on the objective criteria listed below), the patient will be escalated to either intrapleural therapy or surgical intervention according to patient suitability and clinician choice / usual practice.

Treatment applicable to both arms

A number of treatments should be considered best practice and routine management in patients with pleural infection and will be applied to both groups (intervention and standard care). These treatments follow the NHS standard of care for pleural infection and are as follows:

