13.2. Sample Size Determination

As a feasibility study, 30 patients are considered sufficient to demonstrate the feasibility of recruitment to a larger study. In addition, a potential sample size calculation for a definitive phase 3 trial is presented below to ensure the correct feasibility parameters of the recruitment rate are robustly addressed in the feasibility study.

The average hospital stay for pleural infection is 14 days (SD 10). Assuming RAPID driven treatment overall reduces hospital stay by 4 days (as 50% of the RAPID arm will be in the low-risk group and reducing the length of stay by 8 days is reasonable as such patients will be sent home within 24 to 48 hours of treatment), and assuming a clinically meaningful difference in hospital stay of more than 4 days

(SD 10 from previous studies), with 5% significance and 90% power, this would require 264 patients in total (132 randomised 1:1). In a definitive study of this design recruiting in 15 centres in the UK over 18 months recruitment, a rate of 1 patient/centre/month would provide sufficient patients.

For the feasibility RAPTOR study, a target of 30 patients in total (3-4 centres recruitment over 10 months at 1 patient/centre/month) is therefore reasonable.

This number should be sufficient to conduct meaningful qualitative interviews with patients/carers (in discussion with our qualitative co-applicant) and is also sufficient to show a definitive study is possible, with careful measurement of the number eligible / number consented / number randomised / number completing protocol.

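### The RAPID scoring table that assigns intervention-arm treatment gives the serum albumin cut-off in mmol/L, an impossible unit; g/L is evidently meant

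*Protocol*

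**What the plan says.** Section 7.1 sets out the five RAPID items in Table 1. (Section 13.1.2 has another Table 1, for the progression criteria; it is not the one meant here.) The albumin item scores 0 at "Serum albumin level >27mmol/L" and 1 below 27, again in mmol/L. Serum urea, in the same table, is also given in mmol/L.

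The protocol makes this table the working rule. For the intervention arm, section 7.1 says that the score is "calculated at the time of presentation according to the parameters in Table 1", and the synopsis adds: "The subsequent treatment will be determined by the calculated RAPID score".

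Section 9.7 then divides patients at a total of 0 to 2 against 3 to 7. The lower group has aspiration or a short period of drainage, with early discharge. The upper group has a chest drain, early intrapleural enzyme therapy and a surgical referral. Above a total of 2 there is no further split: "The intermediate and high-risk groups have been combined for the treatment algorithm".

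Albumin is not named anywhere else in the protocol. Other sections mention only general blood tests such as the liver and renal profile, so no second statement of the cut-off corrects the first.

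**The concern.** A threshold that helps to assign treatment should be right in the document that sites follow. Here the number 27 comes with a unit in which serum albumin cannot take values anywhere near 27. The error is in the operative rule of the intervention, and an eCRF field or score calculator built directly from the table could copy it. The planned intervention arm has 15 patients at three or four centres, so a wrongly built field could affect every score calculated with it.

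The likeliest explanation is that the urea unit was repeated further down the column. That is an inference. Damage from reading the PDF is not a plausible cause, because the same wrong unit stands on both albumin rows.

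**Working it through.** **Inputs**
- Albumin cut-off: 27 mmol/L in both rows (section 7.1, Table 1).
- Molar mass of albumin: assumed 66.5 g/mmol, range 65 to 69; not in the protocol.
- Serum albumin met in practice: assumed 10 to 50 g/L; not in the protocol.
- Item scores: urea 0 to 2, age 0 to 2, purulence 0 to 1, infection source 0 to 1, albumin 0 to 1 (Table 1).
- Pathway split: 0 to 2 against 3 to 7 (section 9.7).

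**Step 1: the printed cut-off in g/L.** Mass concentration = molar concentration × molar mass.
- 27 × 66.5 = 1,795.5 g/L
- 27 × 65 = 1,755 g/L
- 27 × 69 = 1,863 g/L

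A litre of water weighs about 1,000 g, so the value is impossible whichever molar mass is used.

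**Step 2: the cut-off evidently meant, in mmol/L.** Molar concentration = mass concentration ÷ molar mass.
- 27 ÷ 66.5 = 0.41 mmol/L (27 ÷ 69 = 0.39; 27 ÷ 65 = 0.42)
- The assumed range of 10 to 50 g/L is 10 ÷ 66.5 = 0.15 to 50 ÷ 66.5 = 0.75 mmol/L.

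The printed cut-off is therefore too high by a factor equal to the molar mass, about 65 to 69. In g/L, 27 falls inside the assumed range. In g/dL it would be 270 g/L, far outside. Only g/L fits.

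**Step 3: check against the table's own bands.** The minimum total is 0 + 0 + 0 + 0 + 0 = 0 and the maximum is 2 + 2 + 1 + 1 + 1 = 7. Table 1 starts its low band at 0 and ends its high band at 7. A total of 0 requires an albumin score of 0 to be attainable. It is attainable with g/L and not with mmol/L, so the table itself shows that mmol/L is not intended.

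**Step 4: where the albumin point matters.** The other four items total 0 to 6.
- Other items 0 or 1: the total is at most 2, so low risk either way.
- Other items 2: the total is 2 or 3, so the albumin point decides the pathway.
- Other items 3 to 6: the total is at least 3, so the combined pathway either way.

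A total of 2 arises in 8 of the 3 × 3 × 2 × 2 = 36 combinations of the other items. This is a count of combinations, not a share of patients; the protocol gives no albumin distribution.

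**Step 5: sample size.** Section 13.2 uses a 4-day difference, SD 10, 5% significance and 90% power. Per arm: 2 × (1.960 + 1.282)² × 10² ÷ 4² = 131.4, rounded up to 132, or 264 in total. This reproduces the protocol's figure. No albumin value enters it.

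**The case against.** The strongest reply is that this is a slip of labelling without consequence. Table 1 is captioned as an existing, cited score. Section 5 says that the investigators' own unit published it and that it uses routinely collected data, and section 9.1 describes the sites as established pleural centres. Clinicians there will compare the laboratory's g/L figure with 27. The number 27 itself is not shown to be wrong. Most of this stands, and it is why the point is minor. It does not remove the error: an approved treatment rule should not rely on each site correcting it silently. Appendix C shows that the sponsor has already amended a comparable slip, in the LDH threshold.

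A reader might infer two stronger claims. The documents support neither.

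- **Every patient scores 1 for albumin, so the total never reaches 0 and some low-risk patients are misassigned.** That follows only if someone converts a laboratory result to mmol/L and accepts an impossible cut-off. The table's own band starting at 0 speaks against such a reading. So does the expected case mix: section 9.7 speaks of "similar numbers of patients in the combined intermediate and high risk group and the low-risk group", and section 13.2 plans on this basis: "as 50% of the RAPID arm will be in the low-risk group".
- **A value of exactly 27 has no score.** As the text reads, neither albumin row includes 27, whereas the urea and age bands leave no value out. But this table's text is visibly damaged by the reading from PDF: cells are split and the non-purulent row is cut short. An or-equal sign may have been lost. Such signs survive in other sections, but that does not show that they survived here. The gap is something to check, not a finding.

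**Conclusion.** Minor, and wrong as written: the unit of a decision threshold in the treatment-assigning table is incorrect. The printed cut-off corresponds to about 1,800 g/L (1,755 to 1,863 g/L), against an evident intention of 27 g/L. The exact conversion rests on an assumed molar mass of 65 to 69 g/mmol, but the conclusion does not depend on where in that range the value lies.

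The practical effect is small, since sites will almost certainly apply 27 as g/L. No misassignment of patients is claimed and no frequency is estimated. The success definition, the progression criteria and the sample size are unaffected.

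**What to change.** In Table 1 of section 7.1, change the unit to g/L in both albumin rows. Make sure that the eCRF field, and any score calculator built from the table, uses g/L. While making the correction, look at the table in the source file and confirm that one of the two rows includes exactly 27; if neither does, assign it to one row after checking the published score.

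The cost is a small correction in the next protocol version and a check of one eCRF field.

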7.2. Embedded Qualitative Interviews design

This involves semi-structured interviews involving (n=12) participants and (n = 6) healthcare professionals (Respiratory or pleural and general or acute medicine physicians). Participants enrolled on the RAPTOR f feasibility study or those declined to participate will be verbally consented for their willingness to participate in in-depth interviews. In addition, up to 6 of the treating healthcare professionals will be interviewed. The interviews will be conducted by a person who will be appropriately trained and delegated. Interviews guide topics for the patient participants and the health care professionals were developed in collaboration with patient and public involvement group. Both patients and healthcare professionals will be consented to the interviews.

8. PARTICIPANT IDENTIFICATION

8.1. Study Participants

All participants with pleural infection fulfilling the inclusion are eligible for the study. Screening logs will be kept, documenting reasons for non-inclusions. The study will aim to randomise 30 patients (in a 1:1 ratio) to receive either RAPID driven treatment or standard care treatment for pleural infection.

8.2. Inclusion Criteria

Adults with confirmed pleural infection requiring admission to hospital with ALL of the following:

- 1. A clinical presentation compatible with pleural infection or infective illness
- 2. A pleural collection on radiology (CXR, ultrasound or CT) with a chest drain in situ or planned
- 3. Pleural fluid features diagnostic of infection which is either:
 - A. purulent or
 - B. gram positive or
 - C. culture positive (pleural fluid or biopsy) or
 - D. acidic with a pH<7.2 or
 - E. low pleural fluid glucose <4.4 mmol/L or 72mg/dL(non-diabetic) or LDH ≥ 900 iu/L **OR**
 - F. (non-fluid criteria) CT findings suggestive of pleural infection (pleural enhancement) or pleural fluid septations on thoracic ultrasound
- 4. Willing and able to give written informed consent

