9.1. Recruitment

This feasibility study aims to recruit 30 patients from 3-4 UK centres (Oxford, Norfolk and Norwich, Plymouth and Royal Devon and Exeter with well-established pleural centres that will enroll eligible patients over 8-10 months. The sites are geographically distributed to ensure the population recruited is diverse and representative of the UK pleural infection population.

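### Inclusion criterion 3E gives one low-glucose threshold in two units that do not convert to each other: 4.4 mmol/L is about 79 mg/dL, and 72 mg/dL is about 4.0 mmol/L

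*Protocol*

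**What the plan says.** Section 8.2 of the protocol lists the inclusion criteria, all of which must be met. The third is introduced by "Pleural fluid features diagnostic of infection which is either" and is followed by alternatives A to F, any one of which is enough. Item E gives the glucose limit as "low pleural fluid glucose <4.4 mmol/L or 72mg/dL(non-diabetic" and adds an LDH of at least 900 iu/L as a further alternative. The Study Participants row of the synopsis (section 3) gives the same item with the same figures.

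The protocol states no conversion factor and does not say which figure takes precedence. The amendment history (Appendix C) records a typographical correction to the LDH limit, which stands in the same item, and lists no change to the glucose figures.

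**The concern.** Item E names one analyte, has one less-than sign and carries one qualifier (non-diabetic). The natural reading is therefore a single cut-off written first in SI and then in conventional units. If so, the two numbers must convert to each other, and they do not.

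The figure matters because it is a decision threshold. It can settle criterion 3 when no other item is met. The count of eligible patients is also the denominator of the recruitment proportion and the randomisation acceptance rate (section 13.1.1), of the primary success definition (section 6) and of the first row of the progression table (section 13.1.2). An ambiguous limit also leaves room for dispute if a participant's eligibility is questioned afterwards, which section 10 allows for.

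**Working it through.** **Inputs.** The two stated limits, 4.4 mmol/L and 72 mg/dL, come from section 8.2, item 3E, and the synopsis. The conversion factor is not in the protocol. It follows from the molar mass of glucose, 180.156 g/mol, a physical constant: 1 mmol/L = 180.156 mg/L = 18.0156 mg/dL. Common roundings of the factor are 18.0 and 18.02.

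**Step 1: try to reproduce the stated mg/dL figure.** mg/dL = mmol/L × factor.
- 4.4 × 18.0 = 79.2
- 4.4 × 18.0156 = 79.3
- 4.4 × 18.02 = 79.3

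None of these gives 72.

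**Step 2: convert the other way.** mmol/L = mg/dL ÷ factor.
- 72 ÷ 18.0 = 4.000
- 72 ÷ 18.0156 = 3.997
- 72 ÷ 18.02 = 3.996

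All round to 4.0, not 4.4.

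**Step 3: could rounding explain it?** Any value that rounds to 4.4 lies between 4.35 and 4.45 mmol/L. These limits convert to 4.35 × 18.0156 = 78.4 and 4.45 × 18.0156 = 80.2 mg/dL, so 72 is out of reach. For 4.4 and 72 to agree, the factor would have to be 72 ÷ 4.4 = 16.4, which is not the factor for glucose.

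**Step 4: size of the gap.** 79.3 − 72 = 7.3 mg/dL, and 4.4 − 4.0 = 0.4 mmol/L. Relative to the lower limit this is 7.3 ÷ 72, about 10%.

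**Step 5: who is affected.** A patient's eligibility turns on the choice of figure only if all of the following hold:
- not diabetic;
- pleural glucose from 4.0 to just under 4.4 mmol/L (72 to just under about 79 mg/dL);
- fluid not purulent, Gram stain and culture not positive, pH not below 7.2, and LDH below 900 iu/L;
- neither of the imaging findings in item F (pleural enhancement on CT or septations on ultrasound).

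The protocol gives no distribution of pleural glucose, so this number cannot be estimated from it.

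**Step 6: what one such patient does to the recruitment proportion.** With 30 randomised and a proportion of at least 50%, there are at most 30 ÷ 0.50 = 60 eligible patients. One patient is then 1 ÷ 60 = 1.7% of the denominator. As an illustration only, suppose that patient declines randomisation. Counting the patient gives 30 ÷ 60 = 50.0%, and not counting the patient gives 30 ÷ 59 = 50.8%. Green in the progression table requires more than 50%, so one patient can change the colour only when the result already sits on the boundary.

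**The case against.** The strongest reply is that the mismatch has no practical effect. Section 9.1 says "This feasibility study aims to recruit 30 patients from 3-4 UK centres", and the centres it names are all in the UK. The mmol/L figure comes first, and the RAPID table in section 7.1 also gives serum urea in mmol/L. If every laboratory reports pleural glucose in mmol/L, all sites apply 4.4 and the mg/dL figure is never used. Read literally, the word joining the two figures makes them alternatives. The looser limit then always governs and 72 mg/dL is redundant. Item F, which admits patients on imaging alone, further reduces the number whose eligibility could depend on glucose.

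Most of this stands as an argument about size. Reporting in mmol/L is plausible but is not stated, so it remains an assumption. The literal reading makes the rule workable, but it leaves a second figure that does nothing and still does not match the first. Neither reading makes the text coherent.

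A reader might go further and infer that 72 mg/dL was the intended limit, that 4.4 mmol/L is the slip, and that every site is therefore applying the wrong cut-off. The protocol does not support this: nothing in it shows which figure was meant, and the likely use of mmol/L in the UK is no evidence for the mg/dL value. Nor does it say that this criterion will be carried into the definitive trial, since it sets out no eligibility criteria for that trial.

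**Conclusion.** The inconsistency is real and appears in both places where the threshold is given. If the two figures are one limit in two units, as the wording suggests, at least one of them is wrong as written. The gap is about 7 mg/dL, or 0.4 mmol/L.

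The practical consequence is minor. It is confined to non-diabetic patients in the 4.0 to 4.4 mmol/L band who meet no other item of criterion 3. It is probably very few patients and possibly none, although the protocol offers no data to confirm that. If all sites report in mmol/L, the defect is one of text and not a source of variation between sites. No sample size or power figure depends on it, and its possible effect on the recruitment proportion matters only at a boundary.

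The arithmetic rests on nothing but the molar mass of glucose. The judgement that few patients are affected rests on the breadth of the alternative items. Which of the two figures is right is left open here.

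**What to change.** The sponsor should check both figures against the source from which the criterion was taken and decide which threshold was meant. A single threshold should then be stated, either in one unit only or in two units that convert correctly. The same wording should appear in section 8.2, in the synopsis and in any eligibility form that repeats it.

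The cost is one figure in two places of the protocol, plus a check of the form, and it can go into the next amendment. If the amended limit differs from the one sites have been applying, the screening log can be checked for patients in the affected band so that the eligible count rests on one rule throughout.
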